Appendix 3. Dermatology Life Quality Index (DLQI) Ages 16 and up		66
Appendix 4. Local Tolerability Scale Assessment		67
Appendix 5. Patient Satisfaction Questionnaire		68
Appendix 6. Protocol Amendment Summary of Changes		70

LIST OF TABLES

Table 1:	Schedule of Assessments	16
Table 2	Tapinarof Cream	31
Table 3:	Laboratory Tests	39
Table 4:	Criteria for Determining the Grade/Severity of Adverse Event Terms Not Specified by the National Cancer Institute CTCAE	49

ABBREVIATIONS

Term	Description
AD	atopic dermatitis
AE	adverse event
AESI	adverse event of special interest
AhR	aryl hydrocarbon receptor
ALT	alanine aminotransferase
Anti-HBc	anti-hepatitis B core antigen
AST	aspartate aminotransferase
BP	blood pressure
BSA	body surface area
BUN	blood urea nitrogen
BWTP	Beijing Wenfeng Tianji Pharmaceuticals
C	collect
CBP	childbearing potential
CFR	Code of Federal Regulations
CTCAE	Common Terminology Criteria for Adverse Events
D	dispense
DLQI	Dermatology Life Quality Index
eCRF	electronic case report form
ET	early termination
FDA	Food and Drug Administration
FSH	follicle stimulating hormone
F-U	follow-up
GSK	GlaxoSmithKline
HBsAg	hepatitis B surface antigen
ICF	informed consent form
ICH	International Council for Harmonisation
IEC	Independent Ethics Committee
IND	Investigational New Drug Application
IRB	Institutional Review Board
ITT	Intention to Treat
IV	intravenous
LOCF	Last Observation Carried Forward

Term	Description
LTS	Local Tolerability Scale
MCH	mean corpuscular hemoglobin
MCHC	mean corpuscular hemoglobin concentration
MedDRA	Medical Dictionary for Regulatory Activities
MCV	mean corpuscular volume
MSDS	Material Safety Data Sheet
Nrf2	nuclear factor-erythroid 2-related factor-2
OC	Observed Cases
PASI	Psoriasis Area and Severity Index
PGA	Physician Global Assessment
PK	pharmacokinetic
PND	postnatal day
RBC	red blood cells
SAE	serious adverse event
SAP	Statistical Analysis Plan
SD	standard deviation
TAMA	therapeutic AhR-modulating agent
TEAE	treatment-emergent adverse event
UNSCH	unscheduled
US; USA	United States (of America)
UV	ultraviolet
WBC	white blood cells
WHO	World Health Organization

SYNOPSIS

Name of Sponsor/Company: Dermavant Sciences GmbH		
Name of Investigational Product: DMVT-505 (tapinarof cream, 1%)		
Name of Active Ingredient: Tapinarof		
Protocol Number: DVT-505-3003	Phase: 3	Country: US and Canada
Title of Study: A Long-Term, Open-Label, Extension Study to Evaluate the Safety and Efficacy of Tapinarof Cream, 1% for the Treatment of Plaque Psoriasis in Adults		
Study Centers: Approximately 100 to 120 sites in the United States (US) and Canada		
Objectives: 
 • To evaluate the safety and tolerability of tapinarof cream, 1% in adults with plaque psoriasis • To describe the efficacy of tapinarof cream, 1% over an extended period of time in adults with plaque psoriasis • To describe the effect of tapinarof cream, 1% on psoriasis symptom severity and the associated impact on daily activities and attitudes in adults with plaque psoriasis 		
Methodology: This is a long-term, open-label, multicenter, study to evaluate the safety and efficacy of topical tapinarof cream, 1% in adults with plaque psoriasis. Subjects in this study completed treatment with tapinarof in 1 of 2 Phase 3 pivotal efficacy and safety studies (Study DMVT-505-3001 or Study DMVT-505-3002). This study will consist of up to 40 weeks of treatment and a 4-week safety follow-up period. At the completion of the Week-12 visit of the pivotal study (Baseline [Day 1] in this study), all eligible subjects will be offered enrollment in the long-term extension study. Study visits during the treatment period for all subjects will occur every 4 weeks (\pm 3 days). Unscheduled visits may occur, as needed. Subjects who withdraw from the study before Week 40 will return to the study center for an Early Termination visit. The total duration of study participation will be approximately 44 weeks. Subjects in the study will be treated based on their PGA score from the Week 12 visit in the pivotal study. Subjects entering with a PGA \geq 1 will receive treatment with tapinarof cream, 1% until they achieve a PGA score of 0, at which time treatment will be discontinued and subjects monitored for durability of response. If disease worsening occurs, as evidenced by a PGA \geq 2, treatment will then be re-initiated and continued until a PGA of 0 is observed. Subjects entering with a PGA of 0 will have treatment discontinued and be monitored for durability of response. If disease worsening occurs, as evidenced by a PGA \geq 2, then treatment will be re-initiated and continued until a PGA of 0 is observed. This treatment and re-treatment pattern of use will be continued until the end of the study (i.e., subjects may receive study treatment up until the Week 40 visit). Study drug will be dispensed to subjects during the study visits and will be administered at home between study visits as instructed by site personnel. Subjects will be instructed to apply study drug once daily to all affected areas, including newly appearing lesions and lesions or affected areas that improve during the study. Subjects will apply sufficient study drug to cover completely each lesion with a thin layer of study drug and will record the time of study drug application in a daily diary provided by the study site. (Note that subjects are allowed, but not required, to treat fingernails, toenails, palms, soles and scalp lesions with study drug; however, efficacy analyses will not include assessment of improvement of psoriasis in these areas). Subjects will be instructed to maintain the approximate dosing time chosen at the beginning of the study for their full study participation. Study drug application instructions will be reviewed at subsequent study visits. During subsequent study visits, subjects will		

apply the daily dose of study drug while at the site, under the supervision of site personnel, after efficacy and safety assessments have been completed, if applicable. The time of the study drug application and assessments will depend on the time of the study visit (either morning or afternoon visit). Therefore, the timing of the study visit may lead to a change from the subject's chosen dosing time; if this occurs, it will NOT be considered a protocol deviation; the subject should resume their chosen dosing time the day following any such study visit study drug application. This should only occur for subjects receiving study treatment.

Rescue medications may be initiated with consultation of the medical monitor.

Sample Size Justification:

The sample size of this study is based on the International Conference on Harmonisation (ICH) E1 guideline on extent of population exposure to assess clinical safety for drugs intended for long-term treatment of non-life-threatening conditions. An estimated 850 subjects who complete Study DMVT-505-3001 or Study DMVT-505-3002 will be enrolled in this study across all regions. A high discontinuation rate is anticipated in this long-term extension study. Approximately 300 subjects are expected to complete the study (up to 40 weeks of treatment).

Number of Subjects (planned):

Approximately 850 subjects ages 18 to 75 years of age

Diagnosis and Main Criteria for Inclusion:

Inclusion criteria:

1. Completed the 12-week treatment period in 1 of the 2 pivotal studies (Study DMVT-505-3001 or Study DMVT-505-3002);
2. Male or female;
3. Female subjects of childbearing potential and male subjects who are engaging in sexual activity that could lead to pregnancy should use one of the following acceptable birth control methods while on study and for 4 weeks after the last exposure to study drug. Acceptable contraception methods are:
 - Female subject or male subject's female partner is surgically sterile (bilateral tubal ligation, hysterectomy, bilateral oophorectomy) for a minimum of 3 months prior to the first dose of study drug
 - Female subject or male subject's female partner has had an intrauterine device in place for at least 3 months prior to the first dose of study drug
 - Double barrier methods (e.g., condom plus diaphragm, condom or diaphragm plus spermicide) starting at least 14 days prior to the first dose of study drug
 - Subjects who claim abstinence as their method of contraception are allowed provided they agree to use a double barrier method (e.g., condom plus diaphragm, condom or diaphragm plus spermicide) should they become sexually active from Screening to 1 month after the last dose of study drug
 - Surgical sterilization of male subject or female subject's male partner (vasectomy) a minimum of 3 months prior to first dose of study drug
 - Female subject or male subject's female partner is taking hormonal contraceptives starting at least 3 months prior to the first dose of study drug. If hormonal contraceptives were started less than 3 months prior to the first dose of study drug, subjects must agree to use a double barrier method (e.g., condom plus diaphragm, condom or diaphragm plus spermicide) from Screening through 3 months after the initiation of hormonal contraceptives.

These allowed methods of contraception are only effective when used consistently, correctly and in accordance with the product label. The Investigator is responsible for ensuring that subjects understand how to properly use these methods of contraception. Non-CBP is defined as premenarchal or premenopausal females with a documented bilateral tubal ligation, bilateral oophorectomy (removal of the ovaries) or hysterectomy, or hysteroscopic sterilization; or postmenopausal females defined as a cessation of menses for at least 12 months without an alternative medical cause. In questionable cases a blood sample with simultaneous follicle stimulating hormone (FSH) > 40 ml/U is confirmatory. Documented verbal history from the subject is acceptable.

Female subjects of CBP must have a negative urine pregnancy test at Baseline (Day 1).

- Capable of giving signed informed consent, as applicable, which includes compliance with the requirements and restrictions listed in the informed consent form (ICF); written informed consent must be obtained prior to any study-related procedures.

Exclusion Criteria:

- Used a prohibited concomitant product or procedure to treat psoriasis during pivotal study
- Had a serious adverse event (SAE) that was potentially related to treatment or experienced an adverse event (AE) that led to permanent discontinuation of treatment in the pivotal study
- History of or ongoing serious illness or medical, physical, or psychiatric condition(s) that, in the Investigator's opinion, may interfere with the subject's completion of the study
- Known hypersensitivity to tapinarof or excipients

Investigational Product, Dosage and Mode of Administration:

Tapinarof cream, 1% is a white to off-white cream containing 1% (10 mg/gram) tapinarof, supplied in 30-gram tubes and is to be self-administered once daily via topical application of a thin layer to affected areas.

Duration of treatment:

Subjects enrolling in this study may receive treatment for up to 40 weeks. The duration of treatment is based on PGA score and disease worsening.

Reference Therapy, Dosage and Mode of Administration:

Not applicable

Criteria for Evaluation:

Efficacy:

5-point static PGA (0 to 4 scale), percent of total body surface area (%BSA) affected, and the Psoriasis Area and Severity Index (PASI)

Functional Outcomes and Quality of Life:

Dermatology Quality of Life Index (DLQI)

Safety:

AEs, clinical laboratory tests, vital signs, physical examinations, and Local Tolerability Scale (LTS)

Study Endpoints:

Safety:

- Incidence, frequency, and nature of AEs and SAEs
- Change over time in clinical laboratory tests and frequency of clinically significant abnormal test results
- Change over time in vital signs and frequency of clinically significant abnormal results
- [REDACTED]

Efficacy:

- Proportion of subjects who experience a PGA ≥ 2 at least one time in the study and the median time from baseline to first worsening (PGA ≥ 2) for subjects entering the study with a PGA score of clear (0)
- Proportion of subjects who achieve a PGA score of 0 at least one time in the study [REDACTED]
- Duration of each treatment episode, defined as time from each treatment initiation/re-initiation to each subsequent treatment success (PGA score of 0).
- [REDACTED]
- Proportion of subjects who never achieve a PGA ≥ 2 throughout the study
- Proportion of subjects who never achieve a PGA score of 0 or 1 throughout the study
- [REDACTED]

- Change and percent change from baseline in %BSA affected by visit (OC and LOCF)
- Change and percent change in PASI score by visit (OC and LOCF)
- Change in disease impact on daily activities, as measured by the DLQI total and individual dimension scores

Statistical Methods:

All study data will be summarized overall and by treatment group in the pivotal studies using descriptive statistics using the intent-to-treat (ITT) analysis set of subjects. Categorical variables will be reported using frequency and percentage (e.g., sex, race). Continuous variables will be reported using number of subjects, mean, standard deviation (SD), median, minimum, and maximum. All safety and efficacy data will be listed by subject.

Demographics, baseline characteristics, and all safety assessments (including LTS assessments), will be analyzed using descriptive statistics. The Kaplan-Meier product limit method will be used to estimate the median time (if estimable) from baseline to first disease worsening and first treatment success. If the median is not estimable (e.g., < 50% of subjects worsen), other methods for estimating the median and/or other percentiles of worsening will be applied. All other efficacy assessments will be analyzed using descriptive statistics.

SCHEDULE OF ASSESSMENTS**Table 1:** Schedule of Assessments

	Visit 1	Phone Call	Visit 2	Visit 3	Visit 4	Visit 5	Visit 6	Visit 7	Visit 8	Visit 9	Visit 10	Visit 11	Visit 12	Long-term Extension Period	
														Week 44 (F-U) Day 309	Other Visits
Procedures and Assessment															
Baseline Day 1	±3 Days	±3 Days	±3 Days	±3 Days	±3 Days	±3 Days	±3 Days	±3 Days	±3 Days	±3 Days	±3 Days	±3 Days	±3 Days	UN SCH ^b	ET ^c
Informed consent	X														
Confirm eligibility	X														
Demographics/ Medical History	X ^d														
Brief physical examination	[X]	X	X	X	X	X	X	X	X	X	X	X	X	X	X
Vital signs (pulse, BP, temperature) ^e	[X]	X	X	X	X	X	X	X	X	X	X	X	X	X	X
Urine pregnancy test (all females of CBP)	[X]	X	X	X	X	X	X	X	X	X	X	X	As needed	X	X
Clinical laboratory tests ^f	[X]	X													
Urinalysis	X														
Photography, if applicable ^g	[X]	X	X	X	X	X	X	X	X	X	X	X	X	X	X
Investigator assessed:^c															
PGA	[X]	X	X	X	X	X	X	X	X	X	X	X	X	X	X
BSA affected ^h	[X]	X	X	X	X	X	X	X	X	X	X	X	X	X	X
PASI	[X]	X	X	X	X	X	X	X	X	X	X	X	X	X	X
LTS ⁱ		X	X	X	X	X	X	X	X	X	X	X	X	X	X

		Long-term Extension Period													
		Visit 1	Phone Call	Visit 2	Visit 3	Visit 4	Visit 5	Visit 6	Visit 7	Visit 8	Visit 9	Visit 10	Visit 11	Visit 12	Other Visits
Week 2 Day 15	Week 4 Day 29	Week 8 Day 85	Week 12 Day 113	Week 16 Day 141	Week 20 Day 169	Week 24 Day 197	Week 28 Day 225	Week 32 Day 253	Week 36 Day 281	Week 40 Day 309	Week 44 (F-U) Day 309				
Procedures and Assessment	Baseline Day 1	±3 Days	±3 Days	±3 Days	±3 Days	±3 Days	±3 Days	±3 Days	±3 Days	±3 Days	±3 Days	±3 Days	±3 Days	UN SCH ^b ET ^c	
Completed by subject: ^e															
DLQI	[X]	X	X	X	X	X	X	X	X	X	X	X	X	X	
LTS ⁱ		X	X	X	X	X	X	X	X	X	X	X	X	X	
Patient Satisfaction Questionnaire														X	
Adverse events	X	X	X	X	X	X	X	X	X	X	X	X	X	X	
Concomitant medication	X	X	X	X	X	X	X	X	X	X	X	X	X	X	
Dispense/collect diary ^j	X	X	X	X	X	X	X	X	X	X	X	X	X	X	
Review diaries for treatment compliance		X	X	X	X	X	X	X	X	X	X	X	X	X	
Dispense/collect study drug ^k	D	C/D	C/D	C/D	C/D	C/D	C/D	C/D	C/D	C/D	C	As needed	C		
Review instructions for study drug application ^l	X	X	X	X	X	X	X	X	X	X					
Study drug application under supervision ^m	X		X	X	X	X	X	X	X	X		X			

BP = blood pressure; BSA = body surface area; C = collect; CBP = child-bearing potential; D = dispense; DLQI = Dermatology Life Quality Index; ET = early termination; F-U = follow-up; LTS = Local Tolerability Scale; PASI = Psoriasis Area and Severity Index; PGA = Physician Global Assessment; UNSCH = unscheduled.

^a Visit to occur at the time of completion of Visit 6 (Week 12) in pivotal study. The last assessment completed as part of the pivotal study will be used as the baseline value for assessments with a bracketed “X.”

^b Subjects who experience disease worsening (PGA ≥ 2) between scheduled study visits may contact the study site to arrange an unscheduled visit (see Section 5.1.5.1). If disease worsening is confirmed, a new treatment course will be initiated.

^c Subjects who withdraw from the study before Week 40 will complete an ET visit.

^d As collected at Screening/Baseline in pivotal study.

- ^e Performed prior to study drug application on study visit days.
- ^f Serum chemistry (including liver chemistry tests) and hematology.
- ^g Photography will be performed in a subgroup of subjects at selected (approximately 20) study centers; this is not required of subjects for participation in the study. Informed consent and photographic release will be required.
- ^h %BSA affected must be performed before PASI. (Note that subjects are allowed, but not required, to treat fingernails, toenails, palms, soles, and scalp lesions with study drug; however, efficacy analyses will not include assessment of improvement of psoriasis in these areas
- ⁱ The LTS assessment is only required to be completed if the subject was applying study drug for the period before the current visit.
- ^j Study diary should only be dispensed if study product is dispensed.
- ^k Subjects will be monitored for disease worsening (PGA ≥ 2), and study drug administration may be started at any time during the observation period (see Section **5.1.5.1**)
- ^l Subjects will be instructed to apply study drug once daily at the approximate same time each day, based on subject preference. This should only occur for subjects receiving study treatment.
- ^m Study drug will be applied after safety assessments have been conducted, . Subjects will be instructed and reminded on how to apply study drug at each visit, except during the final treatment visit (see Section **5.1.5.3** for additional details on timing of study drug application during study visits). This should only occur for subjects receiving study treatment.

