1.3.1. Risk Assessment

1.3.1.1. Dermatological Adverse Events, Including Skin Irritation or Allergic Reaction

Tapinarof or its excipients may induce skin irritation. Allergic or irritant reactions in the exposed areas may present as erythema, edema, papules, or vesicles. In the event of pronounced skin reaction, spreading of the eczematous reaction beyond the original application site(s) and/or more generalized (remote) skin reactions may be observed.

In the dose-ranging study 203120 in psoriasis, the most frequently reported dermatologic AEs were folliculitis and contact dermatitis. In the dose-ranging study 203121 in AD, the most frequently reported dermatologic AEs were folliculitis and AD. Nonclinical dermal toxicity studies of up to 8% tapinarof for up to 13 weeks indicated local effects are primarily mild to moderate skin irritation that is reversible; tapinarof did not show evidence of sensitization. In initial clinical studies using a different formulation of tapinarof (Formulation C), AEs of skin

hyperpigmentation, application site dermatitis, papular rash, pruritus, contact dermatitis, folliculitis, erythema, and skin burning sensation were reported.

To mitigate these potential risks, subjects with a known or suspected intolerance to tapinarof or its excipients will be excluded from enrollment. Subjects' skin will be evaluated routinely for signs of irritation or allergic reaction, and if needed, study treatment will be interrupted and an appropriate treatment provided. Note that after cessation of exposure, dermatological reactions generally subside spontaneously or with topical treatments.

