6.3.5. Local Tolerability Scale

At each specified study visit and if the subject is receiving study drug, the Investigator (or qualified evaluator) will assess the presence and overall degree of irritation at the application sites, according to the LTS (an example of the LTS is provided in [Appendix 4](#)). The score will ideally represent an ‘average’ across all application sites. To the fullest extent possible, the same Investigator (or designated evaluator) will perform all tolerability assessments for an individual subject throughout the study. If the subject is applying study treatment to “sensitive areas” (e.g., genitals, face, neck, and skin folds), then the degree of irritation for these areas should also be assessed by the investigator.

Additionally, at each specified study visit if receiving study drug, the subject will use a 5-point LTS to assess the presence and degree of burning/stinging and itching at the treatment areas. The score will ideally represent an ‘average’ across all application sites.

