7.2. Visits 2 to 10; Treatment Period

Subjects entering with a PGA ≥ 1 will receive treatment with tapinarof cream, 1% until they achieve a PGA score of 0, at which time treatment will be discontinued and subjects monitored for durability of response. If/when disease worsening occurs, as evidenced by a PGA ≥ 2 , treatment will then be re-initiated and continued until a PGA of 0 is observed. Subjects entering with a PGA of 0 will have treatment discontinued and be monitored for durability of response. If/when disease worsening occurs, as evidenced by a PGA ≥ 2 , treatment will then be re-initiated and continued until a PGA of 0 is observed. Subjects will return to the study site at least every 4 weeks (± 3 Days) during the 40-week monitoring period. The following assessments will be performed:

- Brief physical exam
- Vital signs measurements
- Urine pregnancy test (females of CBP)
- Blood sample collection for clinical laboratory tests (serum chemistry, hematology, diagnostic tests); Weeks 4, 12 only
- Photography of a representative area of the subject's disease area (optional for subjects; at a subset of study centers)
- PGA score
- BSA affected calculation
- PASI
- LTS (if patient has been applying study drug for the treatment period prior to the scheduled visit)
- DLQI
- AE recording
- Concomitant medication recording
- Collect and dispense diary, if applicable (subjects will be instructed in how and when to complete diary)
- Review diary for treatment compliance, if applicable
- Dispense and collect study drug, if applicable
- Instruction on how to apply study drug, if applicable
- Study drug application under supervision, if applicable

7.3. Visit 11;

The following procedures and assessments will be performed at the Week 40 Visit:

- Brief physical exam
- Vital signs measurements

- Urine pregnancy test (females of CBP)
- Blood sample collection for clinical laboratory tests (serum chemistry, hematology, diagnostic tests)
- Urinalysis
- Photography of a representative area of the subject's disease area (optional for subjects; at a subset of study centers)
- PGA score
- BSA affected calculation
- PASI
- LTS (if patient has been applying study drug for the treatment period prior to the scheduled visit)
- DLQI
- Patient Satisfaction Questionnaire
- AE recording
- Concomitant medication recording
- Collect diary, if applicable
- Review diary for treatment compliance, if applicable
- Collect study drug, if applicable

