APPENDIX 4. LOCAL TOLERABILITY SCALE ASSESSMENT

At each specified study visit, the investigator (or qualified evaluator) will assess the presence and overall degree of irritation at the application sites, according to the 5-point scale. The score will ideally represent an ‘average’ across all application sites. To the fullest extent possible, the same investigator (or designated evaluator) will perform all tolerability assessments for an individual subject throughout the study.

If the subject is applying study treatment to “sensitive areas” (e.g., genitals, face, neck, and skin folds), then also assess the degree of irritation for these areas.

Local Tolerability – Dryness, Erythema, and Peeling

Score	Severity	Description
0	No irritation	No evidence of local irritation/intolerance
1	Mild	Minimal erythema and/or edema, slight glazed appearance
2	Moderate	Definite erythema and/or edema with peeling and/or cracking but does not require treatment modification
3	Severe	Erythema, edema glazing with fissures, few vesicles or papules
4	Very Severe	Strong reaction spreading beyond the treated area, bullous reaction, erosions

At each specified study visit, the subject will use a 5-point tolerability scale to assess the presence and degree of burning/stinging and itching at the treatment areas. The score will ideally represent an ‘average’ across all application sites.

Local Tolerability – Burning/Stinging and Itching

Score	Severity	Description
0	None	Normal, no discomfort
1	Slight	An awareness, but no discomfort and no intervention required
2	Mild	A noticeable discomfort that causes intermittent awareness
3	Moderate	A noticeable discomfort that causes intermittent awareness and interferes occasionally with normal daily activities
4	Strong/Severe	A definite continuous discomfort that interferes with normal daily activities

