11.11.2 Local Tolerability Scale (LTS)

LTS scores will be summarized by visit and DB treatment group for subject overall assessment (scores from 0=None to 4=Strong/Severe) and Investigator overall assessment (scores from 0=No irritation to 4=Very Severe) separately. LTS scores at the sensitive areas will be summarized by visit, area and DB treatment group for Investigator overall assessment as well as listed in a by-subject and by anatomical site listing.

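### The protocol states three different conditions for completing the Local Tolerability Scale, and a reaction that interrupts treatment can be absent from every planned LTS table

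*Protocol*

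**What the plan says.** The protocol states the condition for completing the LTS in three ways.

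- **Past application.** Table 1 footnote i: "The LTS assessment is only required to be completed if the subject was applying study drug for the period before the current visit". Section 7.2 has a near-equivalent, "LTS (if patient has been applying study drug for the treatment period prior to the scheduled visit", and 7.3 (Week 40), 7.6 (unscheduled visits) and 7.7 (Early Termination) repeat it.
- **Current treatment.** Section 6.3.5, investigator scale: "At each specified study visit and if the subject is receiving study drug, the Investigator (or qualified evaluator) will assess" irritation. For the other scale, "at each specified study visit if receiving study drug, the subject will use a 5-point LTS".
- **No condition.** Appendix 4: "At each specified study visit, the investigator (or qualified evaluator) will assess the presence and overall degree of irritation at the application sites".

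The protocol also provides for interruption. Section 1.3.1.1 says that "if needed, study treatment will be interrupted and an appropriate treatment provided". Section 4.6.2 names skin irritation as the one exception to its rule that a treatment course has no temporary stops. Section 8.1.3 allows drug to be stopped for contact dermatitis, folliculitis or headache and restarted on resolution. It also asks sites to bring in, if possible, a subject who reports significant irritation between visits.

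On analysis, SAP 11.11.2 states that "LTS scores will be summarized by visit and DB treatment group", separately for the two scales. SAP 10.5 limits unscheduled visits to listings and renumbers an Early Termination visit as the next nominal visit. SAP 8 states observed-case and LOCF handling for efficacy endpoints only.

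**The concern.** Tolerability is part of the study's first objective, and the LTS is its dedicated scale. If a score is required only while drug is being applied, and irritation is a reason to stop applying it, then whether a score exists depends partly on what it would have been. By-visit summaries would then describe mainly subjects who still tolerate the cream. Because the conditions differ, who is scored could also vary with the section a site follows.

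**Working it through.** The documents state no LTS mean, interruption rate or precision target, so there is no planned figure to reproduce. The check is a comparison of text, followed by arithmetic for illustration.

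**Step 1. Apply each condition to four kinds of subject.**

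| Subject at a scheduled visit | Section 6.3.5 | Footnote i and Section 7 | Appendix 4 |
|---|---|---|---|
| Applied drug up to the visit | scored | scored | scored |
| Applied for part of the interval, then paused for irritation | not required | unclear | scored |
| Paused for irritation for the whole interval | not required | not required | scored |
| Off drug because PGA = 0, no application in the interval | not required | not required | scored |

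The middle two rows are the problem. The last row is a sensible exclusion under 6.3.5 and footnote i, because scoring those subjects would only dilute the summary.

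**Step 2. Ask whether the unscored subjects differ from the scored ones.** Appendix 4 describes investigator grade 2 as not calling for a change in treatment, so an interruption for irritation points to grade 3 or 4 when it is made. Section 8.1.3 ties restart to resolution, so a subject still off drug at a visit may well have an unresolved event. Against this, Section 1.3.1.1 says reactions usually settle once exposure stops.

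**Step 3. Follow one reaction through to the tables.** A subject reacts between visits, attends an unscheduled visit and is scored there under 7.6, then pauses drug. The unscheduled score goes to a listing only (SAP 10.5). At the next scheduled visit the subject is in row 2 or row 3 above. If no score is taken, the reaction appears in no LTS table, because SAP 11.11.2 has no worst score per subject.

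**Step 4. Illustrate the size (all inputs assumed).** Let m0 be the mean among scored subjects, f the share of treated subjects who are paused and unscored, and s the score they would have had.

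Mean over all treated = (1 − f) × m0 + f × s, so the understatement is f × (s − m0).

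| m0 | s | f = 1% | f = 5% | f = 10% |
|---|---|---|---|---|
| 0.2 | 3 | 0.01 × 2.8 = 0.028 | 0.05 × 2.8 = 0.14 | 0.10 × 2.8 = 0.28 |
| 0.5 | 3 | 0.01 × 2.5 = 0.025 | 0.05 × 2.5 = 0.125 | 0.10 × 2.5 = 0.25 |
| 0.5 | 0 | 0.01 × (−0.5) = −0.005 | 0.05 × (−0.5) = −0.025 | 0.10 × (−0.5) = −0.05 |

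The last row is the case where irritation has cleared by the visit: the sign reverses and the effect is small.

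For the share at grade 3 or above, suppose 1% of scored subjects are there. If every unscored subject would be too, the share becomes 0.99 × 1% + 1% = 1.99% at f = 1%, and 0.95 × 1% + 5% = 5.95% at f = 5%. If none would be, it falls slightly, to 0.99% and 0.95%.

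**The case against.** The strongest reply is that the reactions are not lost to the safety record. Local complaints such as burning or redness at the application site are adverse events (protocol 8.1.1). Contact dermatitis and folliculitis are collected in detail (8.1.3) and summarised by maximum grade, duration and action taken, with Kaplan-Meier time to first event (SAP 11.11.1). Interruptions due to adverse events are counted overall and by visit (SAP 11.1). This stands, and it limits the point to the LTS tables. It does not put the missing scores into them.

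The reply can add that the wording differences are loose drafting of one intention, to limit the LTS to subjects on drug, and that footnote i sets what is required without forbidding a score. Both are fair. Neither tells a site what to do with a subject paused partway through the interval.

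Four stronger readings are tempting, and the documents do not support them.

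- **That the bias is certainly downward.** Section 1.3.1.1 expects reactions to subside, so a subject paused for some weeks could score 0.
- **That severe irritation would be reported as 0%.** This needs no subject on drug to score 3 or 4, and nothing in the documents says so.
- **That 6.3.5 scores a subject restarting drug that day without prior exposure.** Table 1 footnote e and Section 7 place assessments before application, so such a subject is not naturally receiving drug when assessed.
- **That Early Termination scores are lost.** SAP 10.5 renumbers those visits into the by-visit tables. The gap there is only for a subject who stopped applying before the visit and so may not be scored.

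**Conclusion.** The inconsistency is real: 6.3.5, footnote i with Section 7, and Appendix 4 give different answers for a subject whose drug is interrupted for irritation. Together with SAP 10.5 and 11.11.2, they allow a reaction to be missing from every LTS table even when the plan is followed as written.

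By-visit LTS results are likely to look somewhat too favourable. That direction rests on unscored subjects still being more irritated than the scored average at the visit. The illustrative shift of 0.03 to 0.28 points rests on assumed values of f, m0 and s. The true size cannot be obtained from the documents, and the study does no statistical testing. The change is worth making because it is cheap and improves a stated safety measure. It does not call the overall safety assessment into question.

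**What to change.** 1. **One trigger, in footnote i, 6.3.5, 7.2, 7.3, 7.6, 7.7 and Appendix 4.** Complete both LTS scales if any study drug was applied since the previous scheduled visit, or if drug is currently interrupted or was withdrawn for a local reaction, even with no application in that interval. Do not require the LTS for other subjects with no application since that visit, such as those off drug because PGA = 0.
2. **SAP 11.11.2, worst score.** Add each subject's worst post-baseline score on the investigator and subject scales, across scheduled, unscheduled and Early Termination visits, among subjects who applied study drug.
3. **SAP 11.11.2, denominators.** Show by visit the number on drug, the number scored, and the number unscored because of interruption. This replaces the assumed f above with an observed count and lets a reader bound the effect.

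The cost is wording in seven places, a few more scale completions at visits that already take place, one extra table per scale and three count rows in the by-visit tables. If the protocol can no longer change, items 2 and 3 can still be done with the data collected, although they cannot recover scores never taken. No dosing or interruption rule changes.
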